adverse events were described for 56% and 62%, respectively). Radium-223 dichloride was authorized in the European Union as Xofigo[®] in November 2013.

Sub-analysis from ALSYMPCA revealed in addition to the improvement in overall survival a pronounced potential for pain reduction, prolonged time to use of external beam radiation therapy (EBRT) for pain palliation and time to opioid use [14]. The distinct reduction of local symptoms from bone metastases delayed substantially the distortion of quality of life (QoL) compared with placebo [15]. This pronounced reduction in tumor related symptoms is an important benefit for patients in the castration resistant stage of prostate cancer where cure is not an option anymore but good symptom palliation the main focus of any treatment.

The effect of Radium-223 on pain and QoL preservation in mCRPC patients was, as described, to some extent demonstrated in the pivotal Phase 3 ALSYMPCA trial. However, this trial was conducted in a closely defined patient population according to strict inclusion and exclusion criteria. This non-interventional prospective study is to further examine the effect of Radium-223 on pain palliation and bone pain related QoL in mCRPC patients in more detail and in a more heterogeneous patient population under routine daily practice conditions in Germany.

To assess pain, the “Brief pain inventory short form” (BPI-SF) will be used. BPI-SF is a short, self-administered questionnaire with 11 items, which was designed to evaluate the intensity of, and the impairment caused by pain. All BPI-SF items are scored using rating scales. Four items measure pain intensity (pain now, average pain, worst pain, and least pain) using 0 (“no pain”) to 10 (“pain as bad you can imagine”) numeric rating scales, and 7 items measure the level of interference with function caused by pain (general activity, mood, walking ability, normal work, relations with other people, sleep and enjoyment of life) using 0 (no interference) to 10 (complete interference) rating scales [16].

For QoL assessment, the questionnaire “Functional Assessment of Cancer Therapy Quality of Life Measurement in patients with bone pain” (FACT-BP) will be used. The FACT-BP consists of 16 items including general functioning and physical and bone pain and uses a 0-4 Likert-scale; recall period of the questionnaire is 7 days.

8 Research questions and objectives

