9.1.2 Secondary endpoint(s)

The secondary endpoints are:

- **Changes of pain over time** by evaluating the worst pain item as well as the subscale scores for pain severity and pain interference as determined by patient responses on the BPI-SF questionnaire. The worst pain item and subscales will be presented separately for each post-baseline assessment.
- **Changes in bone pain related quality of life** as determined by patient responses on the bone pain specific FACT-BP questionnaire. The FACT-BP score will be presented separately for each post-baseline assessment.
- **Pain control rate** as determined by the worst pain item on the BPI-SF patient questionnaire. Pain control is defined as no increase by two points from the baseline BPI-SF worst pain score.
- **Pain progression rate** as determined by the worst pain item on the BPI-SF patient questionnaire. Pain progression is defined as an increase by two points from the baseline BPI-SF worst pain score at any post baseline assessment.
- **Time to first pain progression** is defined as the time between the first injection of Radium-223 until an increase in the BPI-SF worst pain item by at least two points.
- **Time to first opioid use** in patients who did not take opioids at study entry is defined as the time from first injection of Radium-223 until first intake of opioid analgesics.
- **Evaluation of covariates on pain response** of mCRPC patients during treatment with Radium-223. The following covariates will be analyzed:
 - opioid use
 - assessment of extent of bone metastases (<6, 6-20, > 20, superscan)
 - location of bone metastases
 - level of alkaline phosphatase at baseline (<150 mU/l, 150-300 mU/l, and >300 mU/l)
 - PSA level at baseline (<50 µg/l, 50-200 µg/l, and >200 µg/l)
 - WHO pain score at baseline (WHO-Score 0+1 and WHO-Score 2+3)
 - pretreatment with chemotherapy (yes/no)
 - pretreatment with deep androgen ablation by treatment with abiraterone or enzalutamide (yes/no)
 - extent of bone uptake in known lesions (only faint, higher uptake, and strong uptake compared to surrounding bone)

- **Relation between bone uptake in known lesions and pain palliation** (only in patients with bone scan prior to start of treatment and a second scan during or within 6 weeks after end of Radium-223 treatment)
- For **Radium-223 treatment patterns** dosage and number of injections of Radium-223 will be analyzed.

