9.7.4 Analysis of primary outcome(s)

The primary analysis of pain response will be summarized in the population of patients with a score >1 (0="no pain") for the baseline measurement of the 'Worst Pain'-item of the BPI-SF. For each post-baseline assessment, the incidence proportion will be provided, along with the exact 95% confidence

interval. Pain response is defined as an improvement of two points from the baseline BPI-SF worst pain score at any post-baseline assessment, which is considered clinically meaningful [17].

Further details will be given in the SAP.

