9.7.5 Analysis of secondary outcome(s)

- Change of pain over time: The responses to each of the BPI-SF items and the following two dimensions which are aggregated from BPI-SF items will be summarized descriptively:
 - Pain severity index:

It uses the sum of the four items on the pain intensity. All four severity items must be completed for aggregating the pain severity index.
 - Pain interference index:

It uses the sum of the seven pain interference items. The pain interference index is scored as the mean of the item scores multiplied by seven, given that at least four of the seven items have been completed.

Summary statistics, including mean and change from baseline, will be provided for each assessment time point. For the summary of each post-baseline assessment, patients will be excluded if there is no corresponding post-baseline measurement.

- For bone pain related quality of life assessment summary statistics including mean and change from baseline will be provided for each assessment time point of the FACT-BP questionnaire. For the summary of each post-baseline assessment, patients will be excluded if there is no corresponding post-baseline measurement.
- Pain control rate will be summarized. Pain control is defined as no increase by two or more points from the baseline measurement of the ‘Worst Pain’-item of the BPI-SF (Question 3) at any post-baseline assessment.
- Pain progression rate will be summarized. Pain progression is defined as two or more points increase from the baseline measurement of the ‘Worst Pain’-item of the BPI-SF (Question 3) at any post-baseline assessment.
- Time to first pain progression will be summarized by Kaplan-Meier (KM) estimates.
- Pain response will be additionally summarized descriptively for the subgroups defined in ‘evaluation of covariates on pain response’ in Section 9.1.2.

An analysis of covariance model will be used to assess changes in pain severity, as measured by the worst pain score on the BPI-SF, at each post-baseline assessment time point. The baseline worst pain score will be used as a covariate in each analysis of covariance model.

- The relation between bone uptake in known lesions and pain palliation will be analyzed (only in patients with bone scan prior to start of treatment and at least one further documented bone scan during or after end of Radium-223 treatment).

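### Patients with baseline worst pain of 9 or 10 cannot meet the two-point progression definition, so they always count as pain-controlled in three secondary endpoints

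*Protocol*

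**What the plan says.** Section 7 (Introduction) describes the pain intensity items of the BPI-SF, worst pain among them, as scored "using 0 (“no pain”) to 10 (“pain as bad you can imagine”) numeric rating scales".

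Three secondary endpoints rest on a two-point rise in worst pain:

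- **Pain progression rate**, section 9.7.5: "Pain progression is defined as two or more points increase from the baseline measurement of the" worst-pain item, at any assessment after baseline.
- **Pain control rate**, section 9.7.5: "Pain control is defined as no increase by two or more points from the baseline measurement of the" same item. Section 9.1.2 has the shorter form: "Pain control is defined as no increase by two points from the baseline BPI-SF worst pain score".
- **Time to first pain progression**, section 9.1.2: the time from "the first injection of Radium-223 until an increase in the BPI-SF worst pain item by at least two points". Section 9.7.5 adds: "Time to first pain progression will be summarized by Kaplan-Meier (KM) estimates".

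Section 9.7.1 admits to the pain analyses every patient with an evaluable questionnaire at baseline and at least one later visit. Section 9.2.2 requires symptomatic bone metastases and sets no upper limit on pain. The only restriction by baseline score is in section 9.7.4, where the primary pain response is summarised "in the population of patients with a score >1" on the worst-pain item. That rule is stated for pain response alone.

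**The concern.** An endpoint defined by a fixed rise on a bounded scale cannot occur in patients who start too close to the top. Here those are the patients in most pain. One who stays at 10 throughout treatment is reported as pain-controlled, because the scale has no room to record anything worse.

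The protocol already has a restriction with the matching effect at the other end. The rule in section 9.7.4 removes scores 0 and 1, exactly those from which a two-point improvement is impossible. There is no counterpart for worsening. The resulting error runs in one direction only, towards a better-looking result, and it affects the control rate, the progression rate and the progression-free curve together. A reader comparing these figures with historical data, which section 9.9 names as the only external comparison available, would not see how much of the control rate is fixed by the scale.

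**Working it through.** **Inputs from the protocol.** Worst pain runs from 0 to 10 (section 7). The event is a rise of 2 or more (sections 9.1.2 and 9.7.5). Evaluable patients: 70% of 300 = 210 (section 9.5).

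**The plan's own figure.** Table 3 is the only numerical planning result, and it concerns pain response. The normal-approximation interval p ± 1.96 × √(p(1 − p)/210) reproduces it. At p = 0.60, 1.96 × √(0.24/210) = 0.066, so the limits are 0.534 and 0.666, as printed. All nine pairs of limits agree to three decimals. Table 3 is not in dispute and serves below only as a yardstick. The protocol gives no figure for control, progression or time to progression.

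**Step 1: who can have the event.** The largest possible rise is 10 − baseline.

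| Baseline | Largest rise | Can progress? | Largest fall | Can respond? |
|---|---|---|---|---|
| 0 | 10 | yes | 0 | no |
| 1 | 9 | yes | 1 | no |
| 2 to 8 | 8 to 2 | yes | 2 to 8 | yes |
| 9 | 1 | no | 9 | yes |
| 10 | 0 | no | 10 | yes |

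The >1 rule in section 9.7.4 removes exactly the two rows that cannot respond. Nothing removes or flags the two rows that cannot progress.

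**Step 2: effect on the two rates.** Let s be the share at baseline 9-10 and c the control rate among those able to progress.

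- Reported control = s + (1 − s) × c
- Reported progression = (1 − s) × (1 − c)
- Shift in either rate = s × (1 − c)

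Neither s nor c is in the protocol, so both are assumed.

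| s | c = 50% | c = 60% | c = 70% |
|---|---|---|---|
| 5% | 52.5% | 62.0% | 71.5% |
| 10% | 55.0% | 64.0% | 73.0% |
| 12% | 56.0% | 64.8% | 73.6% |

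Example: 0.12 + 0.88 × 0.60 = 0.648. If s = 0 there is no effect.

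**Step 3: is 5-12% a reasonable range for s?** Suppose baseline worst pain is roughly normal with mean 5.5 and SD 2 to 2.5 (assumed), rounded to whole scores. Among scores above 1, the share at 9-10 is:

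- 5.7% to 8.7% if the distribution is cut at 0 and 10;
- 6.2% to 10.0% if it is cut at −0.5 and 10.5;
- 6.8% to 12.2% if out-of-range values are moved to the end scores.

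That is about 6-12%. Without the >1 filter, which section 9.7.4 does not apply to these endpoints, the overall range is 5.5% to 11.5%. In a group of 210, a share of 5-12% is about 10 to 25 patients.

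**Step 4: effect on the Kaplan-Meier median.** Assume exponential times with median m among those able to progress. Then S(t) = s + (1 − s) × 2^(−t/m), and the overall median is −m × log₂[(0.5 − s)/(1 − s)]. With m = 4 months (assumed):

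- s = 5%: −4 × log₂(0.45/0.95) = 4.3 months
- s = 10%: −4 × log₂(0.40/0.90) = 4.7 months

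**Step 5: does another rule catch these patients?** Section 9.7.1 keeps patients in the analyses until their opioid intake increases and does not say that an increase counts as progression. A patient at 9-10 who needs more opioid therefore leaves without an event. The rule does not repair the ceiling.

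**The case against.** The strongest reply is that nothing is biased relative to what the protocol defines. The study is single-arm and descriptive, and it is true of a patient who stays at 9 that he had no two-point rise. Restricting to baseline 8 or less describes a different group and drops the patients in most pain from a study meant to reflect routine practice. This stands as a reason to show both figures and not to replace one with the other. It does not answer the difficulty that, for some patients, the reported status is fixed before treatment starts.

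A second reply is that supportive subsets belong in the SAP, which is not shown and could add one. That is possible. But the protocol itself fixes these definitions, and it set the restriction by baseline score itself for the primary endpoint.

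A third reply is size. At s = 5-12% and c = 60% the shift is 2 to 4.8 percentage points, below the 6.6-point half-width in Table 3 for a 60% rate with 210 patients. This also stands, though a systematic shift is not made harmless by sampling error, and it does not shrink with more patients.

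Three stronger readings are tempting and not supported:

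- A reader might infer that comparisons by opioid use or WHO pain score are distorted. Sections 9.1.2 and 9.7.5 specify those subgroups for pain response, and patients at 9-10 can respond. Only general wording in sections 9.7.1 and 9.7.8 could extend them to control or progression, and any clustering of high scores in particular subgroups is undocumented.
- A reader might treat it as an error that control and progression in section 9.7.5 are complements. It is a redundancy: both rates are correct and carry the same information.
- A reader might take the >1 rule as a stated safeguard against impossible responses. Section 9.7.4 gives no reason for it; only its effect is certain.

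**Conclusion.** The point holds for pain control rate, pain progression rate and time to first pain progression. Its direction follows from the scale and the definitions alone whenever any evaluable patient starts at 9 or 10 and some of those able to progress do so: control is raised, progression lowered and time to progression lengthened. Its size cannot be taken from the protocol. Under the assumptions shown it is modest, about 2 to 5 percentage points on a 60% control rate and 0.3 to 0.7 months on a 4-month median, and it would be negligible if few patients start at 9-10.

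The endpoints are secondary and descriptive. A reader might infer that the primary result is also inflated; it is not, because a fall of two points is possible from 9 and 10. The change is worth making because it is cheap and the rule as written can only flatter the result.

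**What to change.** Add to section 9.7.5 that pain control rate, pain progression rate and time to first pain progression are also given for patients with baseline worst pain of 8 or less, that is, those able to progress. Place them beside the all-patient figures and state the number at baseline 9-10. Present control and progression together as complements.

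Two alternatives are less suitable. Counting an opioid increase as progression, or judging control only at the last assessment, would change the endpoint; the first would also have to be reconciled with the opioid rule in section 9.7.1.

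The cost is a sentence or two of text, with no new data. The added analysis has a slightly smaller denominator: with 210 evaluable patients and 5-12% at 9-10, about 185 to 200 remain. At a 60% rate the half-width of the interval goes from 6.6 points to at most 1.96 × √(0.24/185) = 7.1 points. The all-patient figures lose nothing.

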9.2 Setting

The study will be conducted in nuclear medicine clinics and practices throughout Germany. Data will be collected from approximately 300 patients. The observation period for each patient enrolled in this study is the time from start of therapy with Radium-223 until death, withdrawal of consent, loss to follow-up or regular end of the study which is defined as two years after the last administration of Radium-223 (whatever comes first in time).

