If within routine clinical practice, data will be collected from a follow-up visit approximately one month after end of treatment. Typical information to be collected at this follow-up visit after treatment includes:

- Date of visit
- Patient questionnaires on pain (BPI-SF) and QoL (FACT-BP) filled out by the patient
- WHO pain score
- ECOG status
- Changes in pain medication
- Changes in anti-cancer therapy
- Bone Scan, if available
- Laboratory parameters including ALP, PSA, and blood counts
- Adverse events up to 30 days after last treatment
- Symptomatic skeletal events

Long-term follow-up

For long term follow-up either the patient or treating physician can be contacted by phone, mail or email every three months after end of treatment until death, patient's withdrawal, loss to follow-up, or end of study (whatever comes first in time) for a maximum of two years. Typical information to be collected at long-term follow-up includes:

- Date of follow-up
- Survival status
- Opioid use after last administration of Radium-223 yes/no, if yes, date of first use (only in patients without prior opioid use)
- Symptomatic skeletal events
- Further anti-cancer therapy

End of Observation

The reason for end of observation is documented which could occur at end of study, if the patient died, withdrew his consent or is lost to follow up. In case of death date of death and primary cause of death have to be documented.

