9.3.1 Variables to determine the primary endpoint(s)

The variables for primary objectives are:

- Pain severity will be measured using the worst pain score of the BPI-SF questionnaire. The BPI-SF will be administered prior to each injection of Radium-223 and, if within routine clinical practice, at a follow-up visit approximately one month after the last injection of Radium-223.

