9.3.2 Variables to determine the secondary endpoint(s)

The outcome variables for secondary objectives are:

- Change of pain over time: In addition to pain severity, the subscales of the BPI-SF questionnaire will be evaluated: **The total pain severity subscale** of the BPI-SF is based on the sum of the four items least, worst, average, and current pain. **The pain interference subscale** of the BPI-SF is based on the seven pain interference items.
- Quality of Life: Bone pain related QoL will be measured by evaluation of the total score of the FACT-BP questionnaire. The questionnaire will be filled out together with the BPI-SF prior to each injection of Radium-223 and, if within routine clinical practice, at a follow-up visit approximately one month after the last injection of Radium-223.
- Pain control rate, pain progression rate, and time to first pain progression will be measured using the worst pain score of the BPI-SF questionnaire.
- Evaluation of covariates on pain response:
 - opioid use
 - number of known bone metastases (<6, 6-20, > 20, superscan) at baseline based on the latest bone scintigraphy before the first injection of Radium-223 (not older than 8 weeks)
 - location of bone metastases based on bone scintigraphy
 - level of alkaline phosphatase at baseline (<150 mU/l, 150-300 mU/l, and >300 mU/l)
 - PSA level at baseline (<50 µg/l, 50-200 µg/l, and >200 µg/l)
 - WHO pain score at baseline (WHO-Score 0+1 and WHO-Score 2+3)
 - pretreatment with chemotherapy (yes/no)
 - pretreatment with deep androgen ablation by treatment with abiraterone or enzalutamide (yes/no)
 - bone uptake in known lesions (only faint, higher uptake, and strong uptake compared to surrounding bone)
- location of bone pain
- Radium-223 treatment patterns will be analyzed using dosage, number of treatments and time between treatments
- Course of blood counts

- Treatment-emergent Adverse Events (TEAE) including a description of the event, duration, whether the TEAE was serious, intensity, relationship to Radium-223, action taken, clinical outcome. Patients will be monitored for TEAEs using the NCI-CTCAE Version 4.03.
- Tumor treatment(s) starting after the first application of Radium-223
- Symptomatic skeletal event (SSE) (external beam radiation therapy to relieve skeletal symptoms, new symptomatic pathological vertebral or non-vertebral bone fractures, spinal cord compression, or tumor-related orthopedic surgical intervention)
- Date and cause of death

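### Time to first pain progression has no time limit, but the pain score stops at or about a month after the last injection, so censoring may be informative and progression is probably understated

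*Protocol*

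**What the plan says.** Section 9.1.2 gives the endpoint as the "time between the first injection of Radium-223 until an increase in the BPI-SF worst pain item by at least two points". No end point in time is attached. Section 9.3.2 names a single source: "time to first pain progression will be measured using the worst pain score of the BPI-SF questionnaire".

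Section 9.3.1 sets the schedule: "The BPI-SF will be administered prior to each injection of Radium-223 and, if within routine clinical practice, at a follow-up visit approximately one month". That month is counted from the final injection. Section 9.2.7 makes the same condition explicit: "If within routine clinical practice, data will be collected from a follow-up visit approximately one month after end of treatment". Table 2 agrees. It marks the questionnaires at baseline, at further treatment visits and at the follow-up after end of treatment, and leaves the long-term follow-up column empty. In section 9.2.7 the quarterly long-term contacts record survival, first opioid use, symptomatic skeletal events and further anti-cancer therapy.

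Observation itself continues to the "regular end of the study which is defined as two years after the last administration of Radium-223", unless death, withdrawal or loss comes first (section 9.2). The analysis in section 9.7.5 is one line: "Time to first pain progression will be summarized by Kaplan-Meier (KM) estimates".

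**The concern.** Whether pain is measured depends on whether treatment continues. Patients enter with symptomatic bone metastases (section 9.2.2), so worsening pain is a plausible reason for stopping. Take a patient whose pain rises after injection k and who does not receive injection k+1. Unless the conditional visit takes place and its form is completed, his last score dates from before injection k. Kaplan-Meier then censors him as progression-free just as he progresses, although the method assumes that censoring carries no information about the event.

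The example in section 9.7.1 may add to this. It keeps patients in the pain analyses only until opioid intake rises. If that were applied to this endpoint, it too would remove patients as their pain worsens.

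Pain is the study's main subject, and section 9.9 expects results to be set against historical data. A progression curve that is too low would flatter the treatment in that comparison, most of all among patients who stop early.

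**Working it through.** **The plan's own figures.** The protocol states no number for time to pain progression. Its only design calculation, Table 3, concerns pain response with 210 evaluable patients. It reproduces with the normal approximation: at 50%, 0.5 ± 1.96·√(0.25/210) = 0.432 to 0.568. It has no bearing on this point.

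**Coverage of the instrument.** Visits are typically four weeks apart (section 9.2.7). Six injections are assumed; the protocol gives that number only for the phase III trial. Pre-injection forms then fall at weeks 0, 4, …, 20, which is five post-baseline forms. The conditional visit adds one at about week 24. Observation can run about 104 weeks beyond the last injection.

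**Illustration of the bias.** None of these inputs comes from the documents:
- p = 0.08, true risk of progression per 4-week interval
- q = 0.40, share of progressors who miss the next injection and its form
- q0 = 0.08, chance of stopping for unrelated reasons
- f, share of stoppers who complete the post-treatment form
- censoring at the last completed form, and no deaths

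Among patients with a form at the end of an interval, the observed hazard is

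h = p[(1−q)+qf] / {p[(1−q)+qf] + (1−p)[(1−q0)+q0f]}.

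This applies to the first five intervals. In the sixth, everyone has finished treatment, so having a form depends on f alone and the hazard is p.

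True progression: 1 − 0.92⁵ = 0.341 at week 20; 1 − 0.92⁶ = 0.394 at week 24.

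| f | h | Week | Kaplan-Meier | True |
|---|---|---|---|---|
| 0 | 0.048/(0.048+0.8464) = 0.0537 | 20 | 1 − 0.9463⁵ = 0.241 | 0.341 |
| 0.5 | 0.064/(0.064+0.8832) = 0.0676 | 24 | 1 − 0.9324⁵ × 0.92 = 0.352 | 0.394 |
| 0.9 | 0.0768/(0.0768+0.9126) = 0.0776 | 24 | 1 − 0.9224⁵ × 0.92 = 0.386 | 0.394 |
| 1 | 0.0800 | 24 | 0.394 | 0.394 |

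The f = 0 row stops at week 20 because without the visit there is no week-24 form.

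**Range.** A separate simulation (200,000 patients per scenario, unrelated stopping 5% per interval) gave these Kaplan-Meier estimates after five intervals:

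| True value | q | f = 0 | f = 0.5 | f = 0.8 |
|---|---|---|---|---|
| 0.23 | 25% | 0.18 | 0.20 | 0.22 |
| 0.23 | 50% | 0.12 | 0.18 | 0.21 |
| 0.23 | 75% | 0.06 | 0.15 | 0.20 |
| 0.41 | 25% | 0.33 | 0.37 | 0.39 |
| 0.41 | 50% | 0.24 | 0.33 | 0.38 |
| 0.41 | 75% | 0.13 | 0.29 | 0.36 |

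The shortfall runs from about 1 to 28 percentage points. It disappears when q = 0 or f = 1.

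**The case against.** The strongest reply is that the visit about a month after the last injection falls roughly when the next pre-injection form would have been due. It can therefore record the very worsening that ended treatment. Patients already two points up on an earlier form count as events in any case. This stands: bias needs both pain-driven stopping and missed post-treatment forms, and the protocol gives a rate for neither. It does make the visit conditional on routine practice, so full attendance cannot be presumed.

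A second reply is that censoring rules and sensitivity analyses belong in the SAP, and section 9.7.5 ends by deferring further detail there. That also stands, and the lack of a censoring rule is not the point here. Endpoint, schedule and method are all fixed in the protocol, and no censoring rule can recover scores that were never taken.

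Third, censoring deaths pushes the Kaplan-Meier complement upwards as a cumulative incidence, which works against the understatement. The net direction is therefore probable, not certain.

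A reader might also infer that the plan promises a two-year median for this endpoint, or a comparison with the curves for opioid use and skeletal events. It does neither. Medians are specified for next treatment, skeletal events and survival, and no comparison between curves is planned. If patients are censored at the last form, the curve ends there.

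**Conclusion.** The point holds in a limited form. The protocol pairs an open-ended endpoint and a plain Kaplan-Meier summary with an instrument that stops at the last injection or about a month later. Censoring may be informative, and progression is probably understated. It would go too far to say that patients who stop for pain are necessarily lost just before the event, or that the curve is certainly too low; the conditional visit and the effect of deaths rule that out.

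The size is unknown. Under the stated assumptions it ranges from nothing with full attendance, through about 1 point at 90% and 4 points at 50%, to 10 points at week 20 with no visits. Other assumed rates widen the range, as the simulation shows. This is a secondary, descriptive endpoint in a single-arm study, so the matter is a cheap improvement that affects how the curve may be read. It does not touch the primary result.

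**What to change.** In sections 9.1.2 and 9.7.5:

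1. Define the endpoint as pain progression during treatment and up to about one month after the last injection. Censor at the last BPI-SF, end the time axis there, and report the cumulative proportion at the scheduled assessments.
2. Report how many patients stopped Radium-223 without a later BPI-SF, by recorded reason. Section 9.3.6 already collects the reasons.
3. Add a sensitivity analysis that also counts as progression a discontinuation recorded as due to pain worsening, or external beam radiation for skeletal symptoms, when either occurs before the next BPI-SF. Treat death without progression as a competing event, or show it in a separate composite. Counting every death or every disease-related stop as pain progression would change the endpoint.

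The cost is a wording change and one extra analysis of data already collected. The drawbacks are a shorter time axis and possibly a less favourable progression figure.
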